6.5 Dose Modification and Toxicity Management

6.5.1 Durvalumab (MEDI4736) and tremelimumab

For adverse events (AEs) that are considered at least partly due to administration of durvalumab (MEDI4736) the following dose adjustment guidance may be applied:

- Treat each of the toxicities with maximum supportive care (including holding the agent suspected of causing the toxicity where required).
- If the symptoms promptly resolve with supportive care, consideration should be given to continuing the same dose of durvalumab (MEDI4736) or tremelimumab along with appropriate continuing supportive care. If medically appropriate, dose modifications are permitted for durvalumab (MEDI4736) and tremelimumab (see Appendix 1).
- All dose modifications should be documented with clear reasoning and documentation of the approach taken.

In addition, there are certain circumstances in which durvalumab (MEDI4736) or tremelimumab should be permanently discontinued.

Following the first dose of durvalumab (MEDI4736) or tremelimumab, subsequent administration of durvalumab (MEDI4736) or tremelimumab can be modified based on toxicities observed (see Appendix 1). Reductions in the dose administered are not permitted.

Based on the mechanism of action of durvalumab (MEDI4736) or tremelimumab leading to T-cell activation and proliferation, there is the possibility of observing immune related Adverse Events (irAEs) during the conduct of this study. Potential irAEs include immune-mediated enterocolitis, dermatitis, hepatitis, and endocrinopathies. Subjects should be monitored for signs and symptoms of irAEs. In the absence of an alternate etiology (e.g., infection or PD) signs or symptoms of enterocolitis, dermatitis, hepatitis, and endocrinopathy should be considered to be immune-related.

Dose modification recommendations and toxicity management guidelines for immunemediated reactions, for infusion-related reactions, and for non-immune-mediated reactions are detailed in Appendix 1.

In addition, management guidelines for adverse events of special interest (AESIs) are detailed in Section 10.1.3. All toxicities will be graded according to NCI CTCAE v4.03.

6.5.2 Azacitidine/Oral decitabine (ASTX727)

6.5.2.1 Dose Adjustment Guidelines

Drug Substance Azacitidine/Decitabine (ASTX727)

Study Code 15-11430

Edition Number 13.0

Date 09202024

A maximum of 1 dose reduction will be allowed from the original dose. Please refer to **Table 2** for the dose cohorts.

Azacitidine or oral decitabine may be withheld for up to 7 days between the end of 1 cycle and the start of the next cycle to allow hematologic criteria to recover sufficiently for the next cycle to begin.

The maximum number of days that a azacitidine or decitabine dose may be withheld without requiring a dose reduction is 7 days.

The maximum number of days that azacitidine or oral decitabine may be withheld due to unacceptable toxicity before a subject is permanently discontinued from the study is 14 days.

For the purposes of dose adjustments, unacceptable toxicity will be defined as any AE that is deemed by the Investigator to be related to azacitidine or oral decitabine (ASTX727) that poses a medical risk or substantial discomfort to the subject including, but not limited to, Grade 3 or 4 hematologic or non-hematologic toxicity. Subjects should be discontinued after the 3rd episode.

Please refer to Table 6 for the Dose Adjustment Guidelines due to unacceptable toxicity.

Table 6: Dose Adjustments and Dose Delays for Toxicity

Toxicity	Recommendation	
Grade 2 hematologic toxicity causing delay to the planned start of a Cycle	Hold azacitidine or decitabine until ANC & Platelets \geq 1.0x10 ⁹ /L Delay \leq 7 days, resume azacitidine or decitabine at	
Absolute Neutrophil Count (ANC) $< 1.0 \text{ x}$ $10^9/\text{L}$ Platelets $< 75 \text{ x } 10^9/\text{L}$	same dose Delay $8-14$ days, reduce azacitidine ordecitabine by a dose cohort level Delay ≥ 14 days, permanently discontinue azacitidine or decitabine	
Grade 3 neutropenia or thrombocytopenia causing delay to the planned start of a Cycle ANC 0.5-0.99 x 10 ⁹ /L Platelets 25-49 x 10 ⁹ /L	Hold azacitidine or decitabine until ANC & Platelets recover to ANC $\geq 1.0 \times 10^9 / L$, Platelets $\geq 75 \times 10^9 / L$) Recovery in ≤ 7 days, resume azacitidine or decitabine at same dose Recovery in 8–14 days, reduce azacitidine or	

Date 09202024

Edition Number 13.0

Date 09202024	decitabine by a dose cohort level No recovery by 14 days, permanently discontinue azacitidine or decitabine_	
Grade 4 neutropenia or thrombocytopenia causing delay to the planned start of a Cycle ANC $< 0.5 \times 10^9/L$ Platelets $< 25 \times 10^9/L$ For ANC $< 0.5 \times 10^9/L$ The initiation of G-CSF is left at the Investigator's discretion. If initiated administer G-CSF per institutional practice or package insert and continue until ANC recovers to $\ge 2.0 \times 10^9/L$	Hold azacitidine or decitabine until ANC & Platelets recover to \leq Grade 1 (ANC \geq 1.5 x 10^9 /L, Platelets \geq 75 x 10^9 /L) Recovery in \leq 7 days, reduce azacitidine or decitabine by a dose cohort level No recovery by 7 days, permanently discontinue azacitidine or decitabine	
Grade 3 or 4 Nausea or Vomiting Grade 3 or 4 Diarrhea Grade 3 or 4 Fatigue/Asthenia	Hold until resolution to ≤ Grade 1 and provide optimal medical management. If response ≤ 72 hours (3 days), and recovery ≤ 7 days, reduce azacitidine or decitabine by a dose cohort level If event recurs after re-challenge at reduced dose, discontinue azacitidine or decitabine. If no recovery by 7 days, discontinue azacitidine or decitabine.	
Grade 3 or 4 any other non-hematologic toxicity	Hold until resolution to ≤ Grade 1 and provide optimal medical management. If recovery ≤ 7 days, reduce azacitidine or decitabine by a dose cohort level. If event recurs after re-challenge at reduced dose, discontinue azacitidine or decitabine If no recovery by 7 days,	

Date 09202024

Date 0/202021				
	discontinue azacitidine or			
	decitabine			

ANC = absolute neutrophil count; ASCO = American Society of Clinical Oncology; ESMO = European Society for Medical Oncology; G-CSF = granulocyte colony stimulating factor.

Note: The initiation of G-CSF is left at the Investigator's discretion.

Note: Granulocyte colony stimulating factor (G-CSF) should only be utilized in accordance to ASCO or ESMO recommendations.

Note: If Grade 3 or 4 neutropenia associated with fever or Grade \geq 3 thrombocytopenia with clinically significant bleeding occurs at any time, the dose adjustment guidelines for Grade 4 hematological toxicity should be enacted.

Note: If neutropenia is associated with fever and severe diarrhea, subject should be managed appropriately according to the local practice. In case of recurrence of the diarrhea with neutropenia and fever, the continuation of the subject in the study should be discussed on a case-by-case basis with the sponsor's study monitor.

Note: Any Grade 3 or 4 toxicity that is not clinically significant, as judged by the treating physician and/or PI, does not require any dose reductions of azacitidine or decitabine.

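### Three hematologic rules need correcting: the platelet restart value in Table 6's Grade 2 row, the conflict between Table 6 and Section 6.5.2.2, and the two ANC limits in inclusion criterion 9

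*Combined protocol and SAP*

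**What the plan says.** **Table 6, Grade 2 row.** It applies when ANC is below 1.0 or platelets are below 75×10⁹/L and the next cycle is delayed. Release is "Hold azacitidine or decitabine until ANC & Platelets \geq 1.0x10", in units of 10⁹/L. A delay of up to 7 days keeps the dose and 8–14 days lowers it by one cohort level. The last line is "Delay ≥ 14 days, permanently discontinue azacitidine or decitabine".

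**Table 6, Grade 3 and 4 rows.** The Grade 3 row covers "Grade 3 neutropenia or thrombocytopenia causing delay to the planned start of a Cycle" (ANC 0.5–0.99, platelets 25–49). It requires ANC of at least 1.0 and platelets of at least 75. Recovery within 7 days keeps the dose and recovery in 8–14 days reduces it; otherwise "No recovery by 14 days, permanently discontinue azacitidine or decitabine". The Grade 4 row (ANC below 0.5, platelets below 25) requires ANC of at least 1.5 and platelets of at least 75. It reduces the dose on recovery within 7 days; otherwise "No recovery by 7 days, permanently discontinue azacitidine or decitabine".

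**Section 6.5.2.1 text.** It agrees with the Grade 2 and 3 rows: "The maximum number of days that a azacitidine or decitabine dose may be withheld without requiring a dose reduction is 7 days", and the longest time drug "may be withheld due to unacceptable toxicity before a subject is permanently discontinued from the study is 14 days". Only one dose reduction is allowed.

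**Section 6.5.2.2.** Toxicity is defined by the cycle nadir: platelets below 50 or ANC below 1.0×10⁹/L. For patients without reduced baseline counts, the next cycle waits for recovery. Recovery within 14 days brings no dose change, and later recovery brings a reduction. Recovery means regaining half the drop from baseline to nadir.

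**Section 4.1, criterion 9.** The minimum ANC is 1.0×10⁹/L, with 1500 per mm³ in parentheses as its equivalent.

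**The concern.** These are operative thresholds. Sites use them to decide who enters, when the next cycle starts and at what dose. The Grade 2 row appears to apply an ANC figure to platelets, which leaves its platelet hold empty. The two dose-adjustment sections cover the same counts and the same decision, the start of the next cycle, yet can lead to different actions. Because only one reduction is permitted, the section a site reads can use up that reduction or end the drug. The ANC line lets a patient pass one stated limit and fail the other.

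**Working it through.** **1. Grade 2 row (units 10⁹/L).**
- Platelet counts found only in this row: below 75, less 25–49 (Grade 3 row), less below 25 (Grade 4 row) = 50–74.
- Every count in 50–74 is already at or above 1.0, so the release value is met when the hold begins. The other two rows use 75.
- ANC below 1.0 is 0.5–0.99 (Grade 3 row) plus below 0.5 (Grade 4 row). The ANC trigger in row 1 adds nothing of its own.
- Delays of 8–14 days and of 14 days or more overlap at day 14, which is both reduce and discontinue.
- Section 6.5.2.2 works from the nadir. With illustrative baseline 250 and nadir 40, recovery is 40 + 0.5 × (250 − 40) = 145, so a patient at 60 on the planned start day is still delayed. With a nadir that never fell below 50, and ANC never below 1.0, that section imposes no delay.

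**2. Table 6 against Section 6.5.2.2.** Section 6.5.2.2 recovery = nadir + 0.5 × (baseline − nadir) = (nadir + baseline)/2. For platelets this equals Table 6's 75 when baseline = 150 − nadir:
- nadir 30, baseline 120: (30 + 120)/2 = 75 (Grade 3);
- nadir 20, baseline 130: (20 + 130)/2 = 75 (Grade 4).

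In such patients both definitions are met on the same day, so only the dose action can differ:

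| Course | 6.5.2.1 and Table 6 | 6.5.2.2 |
|---|---|---|
| Grade 3, recovered day 5 | same dose | same dose |
| Grade 3, recovered day 10 | reduce | same dose |
| Grade 3, not recovered by day 14 | discontinue | reduce |
| Grade 4, recovered day 5 | reduce | same dose |
| Grade 4, recovered day 10 | discontinue | same dose |
| Grade 4, not recovered by day 14 | discontinue | reduce |

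Away from those baselines the recovery days separate as well. Baseline 250 and nadir 30 give (250 + 30)/2 = 140 against 75. Baseline 100, the eligibility minimum, with nadir 30 gives (100 + 30)/2 = 65 against 75. The difference can also restore agreement. At baseline 250 and nadir 30, if platelets reach 75 on day 10 but not 140 by day 14, both sections reduce.

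The table assumes that both clocks start at the planned cycle start, which Table 6 says and Section 6.5.2.2 does not. It also assumes that the grade on that day equals the nadir grade.

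**3. ANC limit.** One litre is 10⁶ mm³.
- 1.0×10⁹/L ÷ 10⁶ = 1000 per mm³, so the stated equivalence does not reproduce.
- 1500 per mm³ × 10⁶ = 1.5×10⁹/L.
- The same conversion does reproduce the platelet figure in criterion 9: 100×10⁹/L = 100,000 per mm³.
- The contradictory range is 1.0–1.49×10⁹/L.

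**The case against.** **Platelets of 50–74.** A reader might infer that nothing in the protocol effectively holds drug at these counts. The documents do not support that. Section 6.5.2.2 still delays a patient whose nadir was below 50. Appendix 1 holds study drug for Grade 2 non-immune reactions, although its title covers durvalumab and tremelimumab and its reach to decitabine is arguable. The dose steps in the Grade 2 row run on days of delay, so the 1.0 value does not disable them. What stands is that the row's own platelet hold is empty.

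**How often the sections conflict.** A reader might infer that the two sections nearly always disagree, or turn a tally of courses into a rate. Neither is supported. Some courses agree, any tally depends on how nadir grade is matched to grade at planned start, and no patient frequencies are available.

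**DLT removal.** In Section 6.4, Grade 3 or higher non-immune toxicity is a DLT unless excluded. The exclusions for Grade 3 thrombocytopenia and for Grade 3–4 neutropenia require improvement by a grade within 3 days. Grade 4 thrombocytopenia has no exclusion. A DLT ends treatment, so many prolonged cytopenias up to the end of Cycle 2 are already decided. This narrows the conflict mainly to later cycles, and treatment can run to Cycle 12.

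**Discretion and stated maximums.** The note on "Any Grade 3 or 4 toxicity that is not clinically significant" waives reductions only. It leaves the discontinuation conflicts in place and can create a new mismatch if Section 6.5.2.2 still calls for a reduction. The 7-day and 14-day maximums do favor Table 6, but no text says that it governs.

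**ANC limit.** The Eligibility Checklist completed before registration (Section 13.1.2) may settle this in practice. Its content is not in the documents.

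**Conclusion.** All three points hold and should be fixed. The Table 6 platelet hold has no effect at 50–74×10⁹/L on the planned start day. For platelets below 50 or ANC below 1.0×10⁹/L, the two sections can differ between same dose, reduction and discontinuation, mainly after Cycle 2. Eligibility is contradictory for ANC of 1.0–1.49×10⁹/L. The dose comparison rests on the clock and grade assumptions stated with the table and applies to patients without reduced baseline counts.

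A reader might also infer demonstrated harm or damage to the BED assessment. Nothing in the documents shows that restarting below 75 is unsafe, or that these errors alter the BED operating characteristics, the sample size or the analysis.

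**What to change.** 1. Make the Grade 2 row platelet-only (50–74×10⁹/L) with restart at 75×10⁹/L or above. Leave ANC below 1.0 to the Grade 3 and 4 rows, and change the row's last line to more than 14 days.
2. State that Section 6.5.2.1 and Table 6 govern, since they match the stated 7-day and 14-day maximums. Delete Section 6.5.2.2 or align it, leaving one recovery definition and one start day for the count. The clinical team should first check the prescribing-information table that Section 6.5.2.2 cites.
3. Express the criterion 9 ANC limit as one number in both units, either 1.0×10⁹/L (1000 per mm³) or 1.5×10⁹/L (1500 per mm³), chosen by the clinical team.

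The cost is protocol wording and a site notice. There is no statistical cost.

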6.5.2.2 Dose Adjustment Based on Hematology Toxicity

Hematological toxicity is defined as the lowest count reached in a given cycle (nadir) if platelets fall below 50.0×10^9 /L and/or ANC below 1.0×10^9 /L. Recovery is defined as an increase of cell line(s) where hematological toxicity was observed of at least half of the difference of nadir and the baseline count plus the nadir count (ie, blood count at recovery \geq nadir count + [0.5 x (baseline count – nadir count)]. Please refer to the Table in Section 2.3 of the PI.

For Patients Without Reduced Baseline Counts: WBCs \geq 3.0 x 10 9 /L, ANC \geq 1.5 x 10 9 /L, and Platelets \geq 75.0 x 10 9 /L:

If hematological toxicity is observed following azacitidine or decitabine treatment, the next cycle of azacitidine or decitabine therapy should be delayed until the platelet count and the ANC have recovered. If recovery is achieved within 14 days, no dose adjustment is necessary. However, if recovery has not been achieved within 14 days, the dose should be reduced.

Following dose modifications, the cycle duration should return to 28 days.

For Patients with Reduced Baseline Blood Counts: WBC $< 3.0 \times 10^{9}$ /L, ANC $< 1.5 \times 10^{9}$ /L, and Platelets $< 75.0 \times 10^{9}$ /L:

Drug Substance Azacitidine/Decitabine (ASTX727)

Study Code 15-11430

Edition Number 13.0

Date 09202024

Following azacitidine or decitabine treatment, if the decrease in WBC or ANC or platelets from baseline is less than 50%, or greater than 50% but with an improvement in any cell line differentiation, the next cycle should not be delayed and no dose adjustment made.

If the decrease in WBC or ANC or platelets is greater than 50% from that prior to treatment, with no improvement in cell line differentiation, the next cycle of azacitidine or decitabine therapy should be delayed until the platelet count and the ANC have recovered. If recovery is achieved within 14 days, no dose adjustment is necessary. However, if recovery has not been achieved within 14 days, bone marrow cellularity should be determined. If the bone marrow cellularity is \geq 50%, no dose adjustments should be made. If bone marrow cellularity is \leq 50%, treatment should be delayed and the dose reduced). Following dose modifications, the cycle duration should return to 28 days.

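### Table 6 and Section 6.5.2.2 give opposite stop-or-continue actions for azacitidine/decitabine when Grade 3-4 counts delay a cycle, and no text says which rule governs

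*Combined protocol and SAP*

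**What the plan says.** Section 6.5.2.1 defines unacceptable toxicity to include Grade 3 or 4 hematologic events and directs the reader onward: "Please refer to Table 6 for the Dose Adjustment Guidelines due to unacceptable toxicity". In Table 6, the Grade 3 row (ANC 0.5-0.99 or platelets 25-49 x 10^9/L, delaying a cycle) keeps the dose if recovery comes within 7 days and drops one level if it comes on days 8-14. After that: "No recovery by 14 days, permanently discontinue azacitidine or decitabine". The Grade 4 row (ANC below 0.5 or platelets below 25) drops one level if recovery comes within 7 days. Otherwise: "No recovery by 7 days, permanently discontinue azacitidine or decitabine".

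The text of 6.5.2.1 fits that table. It allows a hold of up to 7 days between cycles for counts to recover, and it adds: "The maximum number of days that a azacitidine or decitabine dose may be withheld without requiring a dose reduction is 7 days". The longest that either drug "may be withheld due to unacceptable toxicity before a subject is permanently discontinued from the study is 14 days".

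Section 6.5.2.2 then gives its own rule. It is triggered by any nadir with platelets below 50 or ANC below 1.0 x 10^9/L. The next cycle waits for recovery, defined as an increase "of at least half of the difference of nadir and the baseline count plus the nadir count". For patients without reduced baseline counts, its rule on recovery reads: "achieved within 14 days, no dose adjustment is necessary. However, if recovery has not been achieved within 14 days, the dose should be reduced".

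**The concern.** A patient with Grade 3 or 4 counts on the planned cycle start date meets both triggers, because 6.5.2.2 has no upper grade limit. A site that follows 6.5.2.2 can give more drug to a patient whom Table 6 stops permanently. Two patients with identical counts can be handled in opposite ways.

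Section 1.4.2.5 names myelosuppression as the leading cause of dose reduction and of stopping in azacitidine trials, so this is a foreseeable situation. Safety is the secondary objective, and the adverse event profile helps to choose the expansion dose. Uneven stopping would blur both, in cohorts of six.

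**Working it through.** The plan gives no figure to reproduce here, so the check sets the two rules side by side. It assumes that both clocks start on the planned cycle date and that both recovery definitions are met, or missed, in the same window.

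| Worst grade | First recovery | Table 6 | 6.5.2.2 (baseline not reduced) | Result |
|---|---|---|---|---|
| 3 | day 7 or earlier | same dose | no adjustment | agree |
| 3 | days 8-14 | one level down | no adjustment | dose differs |
| 3 | not by day 14 | stop | reduce | **stop v. continue** |
| 4 | day 7 or earlier | one level down | no adjustment | dose differs |
| 4 | days 8-14 | stop | no adjustment | **stop v. continue** |
| 4 | not by day 14 | stop | reduce | **stop v. continue** |

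The two dose-only differences can be reconciled in some patients, because a Table 6 note waives reductions for Grade 3-4 toxicity judged not clinically significant. That note does not waive discontinuation, so the point rests on the three bold rows.

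**Recovery marks.** Table 6, Grade 4, needs ANC of at least 1.5 and platelets of at least 75. Section 6.5.2.2 needs nadir + 0.5 x (baseline - nadir). The two marks are equal when baseline = 2 x (Table 6 mark) - nadir. With assumed counts (x 10^9/L):

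- ANC nadir 0.4: the marks cross at 2 x 1.5 - 0.4 = 2.6. At baseline 1.5 the midpoint is 0.4 + 0.5 x 1.1 = 0.95, laxer than 1.5. At baseline 4.0 it is 0.4 + 0.5 x 3.6 = 2.2, stricter.
- Platelet nadir 20: the marks cross at 2 x 75 - 20 = 130. At baseline 100 the midpoint is 20 + 0.5 x 80 = 60, laxer than 75. At baseline 250 it is 20 + 0.5 x 230 = 135, stricter.

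**When it arises.** Section 6.4 removes a patient with a DLT from treatment, and its window ends with Cycle 2. In escalation, many of these patients are therefore gone before the conflict appears. Those who can remain include afebrile neutropenia and non-bleeding Grade 3 thrombocytopenia that improve by a grade within 3 days. Section 3.1 runs the window to 28 days after Cycle 2, which could be read as covering Cycle 3. Section 6.4 ties DLT evaluation to the escalation phase, so in the expansion cohort the conflict may arise from Cycle 1.

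**The case against.** The best reply is that the intended rule is not in doubt. The 7-day inter-cycle hold, the 14-day maximum and the referral of Grade 3-4 hematologic toxicity all sit in 6.5.2.1, and all agree with Table 6. Section 6.5.2.2 stands alone. For Grade 4 recovering on days 8-14, its statement that no adjustment is needed can be read as permission, not an order to resume, and Section 4.3 lets the investigator stop for any adverse event.

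Much of this stands. It shows which rule should win, and it keeps the weight of the point moderate. It does not remove the conflict. Section 6.5.2.2 comes later, is headed for hematologic toxicity and names both drugs, and no sentence subordinates it. Past day 14 its instruction is to reduce, which presupposes continuing. Section 6.5.2.3 allows resumption after a toxicity interruption without a time limit, so it does not settle the matter.

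A reader might infer more than the documents support:

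- *That 6.5.2.2 is always the laxer rule.* The marks cross, so at high baselines it is the stricter.
- *That it generally restarts patients while ANC is still Grade 3.* The midpoint is below 1.0 only if baseline ANC is below 2.0 minus the nadir. With nadir 0.4 and baseline at least 1.5, that means 1.5 to just under 1.6.
- *That it undermines the primary objective.* BED is read on the week-8 biopsy. Of the planned cycle starts after Cycle 1, only that of Cycle 2 falls before week 8.
- *That exposure would differ greatly.* The documents give no frequency for such delays and no expected time on treatment. Section 6.5.2.1 also limits patients to one reduction and stops them after a third episode.

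**Conclusion.** The point holds, and it should be fixed. For patients without reduced baseline counts, three of the six grade-by-recovery situations end in permanent discontinuation under Table 6 and in continued treatment under 6.5.2.2, with no stated precedence. The recovery definitions also differ, in a direction that depends on baseline.

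Its reach is limited: mainly Cycle 3 onward in escalation (later if the DLT window covers Cycle 3), and possibly Cycle 1 onward in expansion. The effect on the BED readout is small. The number of patients affected cannot be estimated from the documents. The comparison depends on the common clock and shared recovery window assumed above. The recovery-mark examples use assumed counts.

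**What to change.** Open 6.5.2.2 with: *Table 6 governs hematologic delays, reductions and discontinuation of azacitidine or decitabine.* For patients without reduced baseline counts, delete the midpoint recovery definition and the 14-day dose actions. If the reduced-baseline paragraphs are kept, keep the midpoint definition for them only.

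Choosing Table 6 is a clinical decision with a downside. Patients with high baselines would restart at a lower count: in the Grade 4 examples above, ANC 1.5 instead of 2.2, and platelets 75 instead of 135. Some patients would stop who would have continued under 6.5.2.2.

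Two checks belong with the edit:

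- Confirm how the ANC 1.5 mark applies when baseline ANC is below 1.5. Section 4.1 admits ANC of at least 1.0 x 10^9/L, although its bracket says 1500 per mm³. At baseline 1.2, a patient with Grade 4 neutropenia would have to reach 1.5/1.2 = 125% of baseline within 7 days or stop.
- Check the Grade 2 row of Table 6 against its source. As it reads here, day 14 falls under both reduce and stop, the ANC trigger below 1.0 overlaps the Grade 3 range, and the platelet release value is 1.0 x 10^9/L. Any of these may be a fault of text extraction.

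The cost is wording plus two clinical decisions (Table 6 as the governing rule, and low-baseline ANC). No extra patients, visits or analyses are needed.
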